## 2.2. Internal Administrative Interim Analysis

An administrative interim analysis of efficacy and safety data was performed by the external statistician and reviewed by 2 individuals from Gilead. The purpose of this analysis was to assess the efficacy and safety of selonsertib + prednisolone in alcoholic hepatitis to support further planning and development of selonsertib for this indication. The 2 unblinded individuals from Gilead were independent of the GS-US-416-2124 study team and were not directly involved in routine study conduct. Individuals from Gilead who were unblinded were documented on an unblinding form, and the rationale for performing the internal interim analysis was documented per Gilead standard operating procedures. The Study Team remained blinded to treatment assignment until after the primary analysis (ie, all subjects had completed through the later of their Week 8 study visit, last dose date plus 30 days, or prematurely terminated from study) database had been finalized and the study was unblinded for the primary analysis.

# 2.3. Primary Analysis

The primary analysis was conducted once all subjects completed the later of their safety followup visit 30 days following their last dose of study drug or Week 8 study visit; or they prematurely terminated from study. All data collected with onset/visit dates on/prior to 16 February 2018 (the date the last subject completed their Week 8 visit) were included in the database snapshot for the primary analysis. All outstanding data queries were resolved or adjudicated as unresolvable, and the data was cleaned and finalized. Treatment assignments were unblinded and TFLs were displayed by treatment group.

#### 2.4. Final Analysis

After all subjects complete the study, outstanding data queries will be resolved or adjudicated as unresolvable, and the final analysis of the data will be performed.

# 3. GENERAL CONSIDERATIONS FOR DATA ANALYSES

Analysis results will be presented using descriptive statistics. For categorical variables, the number and percentage of subjects in each category will be presented; for continuous variables, the number of subjects (n), mean, standard deviation (SD), median, first quartile (Q1), third quartile (Q3), minimum, and maximum will be presented.

All statistical tests (PPD ) will be 2-sided and performed at the 5% significance level unless otherwise specified.

By-subject listings will be presented for all subjects in the Safety Analysis Set unless otherwise specified. Listings will be sorted by subject ID number, visit date, and time (if applicable). Data collected on log forms, such as AEs, will be presented in chronological order within the subject. The treatment group to which subjects were randomized will be used in the listings. Age, sex at birth, race, and ethnicity will be included in the listings, as space permits.

#### 3.1. Analysis Sets

Analysis sets define the subjects to be included in an analysis. Analysis sets and their definitions are provided in this section. Subjects included in each analysis set will be determined before the study blind is broken for the primary analysis. The analysis set will be identified and included as a subtitle of each table, figure, and listing.

The number of subjects eligible for each analysis set will be provided by treatment group. Subjects who were excluded from the safety/mITT or FAS analysis sets will be summarized or provided in a by-subject listing.

## 3.1.1. All Randomized Analysis Set

All Randomized Analysis Set includes all subjects who were randomized into the study.

#### 3.1.2. Modified Intent to Treat Analysis Set

The modified Intent to Treat (mITT) analysis set includes all subjects who were randomized and took at least 1 dose of study drug. The mITT analysis set is the same as the safety analysis set provided that all subjects receive their assigned treatment. This will be the secondary analysis set for efficacy analyses.

#### 3.1.3. Full Analysis Set

The Full Analysis Set (FAS) includes all subjects who took at least 1 dose of study drug, and had histologically-confirmed severe AH. This is the primary analysis set for efficacy analyses.

#### 3.1.4. Safety Analysis Set

The Safety Analysis Set includes all subjects who were randomized and took at least 1 dose of study drug. This is the primary analysis set for safety analyses.

#### 3.1.5. Pharmacokinetic Analysis Set

The Pharmacokinetic (PK) Analysis Set will include all randomized subjects who took at least 1 dose of selonsertib and have at least 1 nonmissing postdose concentration value reported by the PK laboratory for selonsertib or the primary metabolite GS-607509.

#### 3.1.6. Pharmacokinetic Substudy Analysis Set

The PK Substudy Analysis Set will include all randomized subjects who took at least 1 dose of selonsertib, participated in the PK substudy, and have at least 1 nonmissing steady state PK parameter for selonsertib or the primary metabolite GS-607509. This is the primary analysis set for detailed PK analysis that uses intensive PK sampling.

# 3.2. Subject Grouping

For analyses based on the mITT and FAS, subjects will be grouped according to the treatment to which they were randomized. For analyses based on the Safety Analysis Set, subjects will be grouped according to their randomized treatment except when their actual treatment differs from randomized treatment for the entire treatment duration. In this case, subjects will be grouped based on actual treatment received.

For the PK Analysis Set, subjects will be grouped according to the actual treatment they received.

#### 3.3. Strata and Covariates

Subjects will be randomly assigned to treatment groups via the interactive web response system (IWRS) in a 1:1 ratio using a stratified randomization schedule. Stratification will be based on the screening MELD score as follows:

- Screening MELD score < 25
- Screening MELD score  $\geq 25$

Subjects enrolled under Amendment 1 of the protocol (eg, Subject IDs PPD and PPD and PPD will utilize Covance laboratory results for calculation of screening MELD score; all other subjects will utilize local laboratory results for calculation of screening MELD score for the purposes of assignment to randomization stratum. Death by Day 28 and by Week 8 will be summarized by randomization stratum as described in Section 3.4. If there are discrepancies in stratum assignment between the IWRS and the calculated value, the stratum assigned based on the database-calculated screening MELD score (as described above) will be used for analysis.

#### 3.4. Examination of Subject Subgroups

Death by Day 28 and by Week 8; and Lille score broken into 3 categories (< 0.16 [complete responder]; 0.16 to < 0.56 [partial responder]; and  $\ge$  0.56 [null responder]) at Week 1, Week 2, and Week 4 (LOCF) will be explored for the FAS by treatment group for the following baseline characteristics:

- age (< 50 or  $\ge$  50 years)
- sex (male, female)
- race (White, Asian, other)
- baseline total bilirubin (< 14 mg/dL,  $\ge 14 \text{ mg/dL}$ )
- baseline prothrombin time (< 16.3 secs,  $\geq$  16.3 secs)
- baseline Maddrey's DF ( $< 38, \ge 38$ )
- baseline albumin (< 3.0 mg/dL,  $\geq 3.0 \text{ mg/dL}$ )
- baseline creatinine (< 0.75 mg/dL,  $\ge 0.75 \text{ mg/dL}$ )
- baseline CPT (scores < 10 [Class A and B],  $\geq$  10 [Class C])
- baseline infection (yes or no)
- baseline sodium (< 135  $\mu$ mol/L,  $\geq$  135  $\mu$ mol/L)
- baseline MELD ( $< 21 \text{ or } \ge 21$ )
- baseline platelets ( $\leq 100 \times 10^3 / \mu L$ ,  $> 100 \times 10^3 / \mu L$ )
- baseline ascites (none, any)
- baseline hepatic encephalopathy (none, any)
- baseline cirrhosis (no, yes, unknown)

Cirrhosis will be determined from the liver biopsy eCRF, and will be defined as a Metavir score of F4 or an Ishak score of F5 or F6. If no fibrosis staging was performed, cirrhosis status will be unknown.

Death by Study Day 28 and by Week 8 will also be explored by the following 2 postbaseline characteristics by treatment group:

- randomization stratum (screening MELD < 25 and  $\geq$  25)
- Lille score broken into 3 categories (< 0.16 [complete responder]; 0.16 to < 0.56 [partial responder]; and ≥ 0.56 [null responder]) at Week 1. Subjects with missing Lille score values at Week 1 will be considered to be null responders.

#### 3.5. Multiple Comparisons

# 3.6. Missing Data and Outliers

#### 3.6.1. Missing Data

In general, missing data will not be imputed unless methods for handling missing data are specified, except for the cases described below.

For subjects who are missing a baseline central laboratory-calculated MELD score, the subject's screening local laboratory-calculated MELD score used to assess inclusion and exclusion criteria and to stratify the subject for randomization will be used in place of the missing central laboratory-calculated baseline MELD score.

For Lille scores, if the Week 1 Lille score for an individual subject cannot be calculated using central laboratory data and a Week 1 Lille score using local laboratory data is available, then Lille scores for that subject will be calculated using local laboratory data for all Lille score timepoints (eg, at Weeks 1, 2, 3, and 4). If both central and local laboratory Week 1 Lille scores are not calculable, then central laboratory data will be used to calculate Lille scores for all visits.

Individual subjects for whom the above imputation rules will be applied will be outlined in the Programming and Analysis Specifications (Appendix 2 of this SAP), along with the reason for their imputation.

For subjects missing a last dose date of study drug, imputation rules are described in Section 4.2.1. The handling of missing or incomplete dates for AE onset is described in Section 7.1.5.2, and for missing start dates for prior and concomitant medications in Section 7.4.

# 3.6.2. Outliers

Outliers will be identified during the data management and data analysis process. All data, including outliers, will be included in analyses.

## **3.7.** Data Handling Conventions and Transformations

In general, age (in years) on the date of the first dose of study drug will be used for analysis and presentation in listings. If a randomized subject was not dosed with any study drug, the baseline assessment date will be used for calculating age. For screen failures, date informed consent was signed will be used for calculating age. If only birth year is collected on the eCRF, "01 July" will be used for the unknown birth day and month for the purpose of age calculation, unless age is captured on the CRF. If only birth month and year are collected on the eCRF, "01" will be used for the unknown birth date for the purpose of age calculations unless age is captured on the eCRF.

Non-PK data that are continuous in nature but are less than the lower limit of quantitation (LOQ) or above the upper LOQ will be imputed as follows:

- A value that is 1 unit less than the LOQ will be used for calculation of descriptive statistics if the datum is reported in the form of "< x" (where x is considered the LOQ). For example, if the values are reported as < 50 and < 5.0, values of 49 and 4.9, respectively, will be used for calculation of summary statistics. An exception to this rule is any value reported as < 1 or <0.1, etc. For values reported as < 1 or < 0.1, a value of 0.9 or 0.09, respectively, will be used for calculation of summary statistics.
- A value that is 1 unit above the LOQ will be used for calculation of descriptive statistics if the datum is reported in the form of "> x" (where x is considered the LOQ). Values with decimal points will follow the same logic as above.
- The LOQ will be used for calculation of descriptive statistics if the datum is reported in the form of " $\leq x$ " or " $\geq x$ " (where x is considered the LOQ).

If methods based on the assumption that the data are normally distributed are not adequate, analyses may be performed on transformed data or nonparametric analysis methods may be used, as appropriate.

Natural logarithm transformation will be used for plasma concentrations and analysis of PK parameters. Plasma concentration values that are below the limit of quantitation (BLQ) will be presented as "BLQ" in the concentration data listing. Values that are BLQ will be treated as 0 at predose time points, and one-half the value of the lower LOQ (LLOQ) at postbaseline time points, where LLOQ is corrected for the dilution factor (ie, reported LLOQ/dilution factor) for determination of summary and order statistics.

The following conventions will be used for the presentation of summary and order statistics:

- If at least 1 subject has a concentration value of BLQ for the time point, the minimum value will be displayed as "BLQ."
- If more than 25% of the subjects have a concentration data value of BLQ for a given time point, the minimum and Q1 values will be displayed as "BLQ."
- If more than 50% of the subjects have a concentration data value of BLQ for a given time point, the minimum, Q1, and median values will be displayed as "BLQ."
- If more than 75% of the subjects have a concentration data value of BLQ for a given time point, the minimum, Q1, median, and Q3 values will be displayed as "BLQ."
- If all subjects have concentration data values of BLQ for a given time point, all order statistics (minimum, Q1, median, Q3, and maximum) will be displayed as "BLQ."

#### 3.8. Analysis Visit Windows

#### **3.8.1. Definition of Study Day**

Study day will be calculated from the date of first dose of selonsertib/placebo (SEL/PLA) study drug as follows:

- For postdose study days: Assessment Date First Dose Date SEL/PLA + 1
- For days prior to the first dose: Assessment Date First Dosing Date SEL/PLA

Therefore, study day 1 is the day of first dose of SEL/PLA study drug administration.

In the event that SEL/PLA and prednisolone (PRED) study drug were not started on the same date, the date of first dose of SEL/PLA will be used as the date of first dose of study drug since subjects are allowed (per protocol Amendment 2) to take "pre-doses" of commercial prednisolone for up to 3 days prior to starting study drug.

The last dosing date for an individual study drug (ie, SEL/PLA or PRED) will be the end date recorded for that study drug on the study drug administration eCRF where the "subject permanently discontinued" flag is marked 'Yes'. The last dosing date for any study drug will be the maximum of the last dosing dates for SEL/PLA and PRED.

If the last dosing date of SEL/PLA or PRED is missing or incomplete, the date of last dose will be estimated using the maximum of nonmissing study drug start or stop dates (for the study drug of interest), visit dates, and laboratory collection dates (posttreatment visits and unscheduled visits are not included).

# 3.8.2. Analysis Visit Windows

Subject visits might not occur on protocol-specified days. Therefore, for purposes of analysis, observations will be assigned to visit windows.

In general, the baseline value will be the last nonmissing value on or prior to the first dose date of SEL/PLA study drug. When the Screening and Day 1 visits are conducted on the same date, the later time value for Covance laboratory values should be used for purposes of analysis since the date/time is prior to first dose date/time from the pharmacokinetic study drug administration (PKEX) eCRF for all 4 subjects (eg, Subject IDs PPD PPD and PPD PPD and PPD PPD

Analysis windows for efficacy measures of hepatic synthetic function (ie, ALT, AST, GGT, alkaline phosphatase, total bilirubin, direct bilirubin, albumin, INR, MELD, CPT, and Maddrey's DF), Lille score and recidivism to alcohol are displayed in column 2 of Table 3-1.

The analysis visit windows for liver fibrosis markers (ie, ELF score and its components) are displayed in the third column of Table 3-1.

The analysis visit windows for safety laboratory tests and vital signs will include laboratory values collected up to last dose date of any study drug + 7 days for "on-treatment" visit windows. Values that are collected  $\geq$  8 days after the last dose date of study regimen will be assigned to follow up visits, where FU day is defined as:

FU Day = Laboratory assessment date – Last Dose Date of Any Study Drug

For analyses of laboratory parameters that are both efficacy and safety variables (eg, hepatic synthetic function tests, and HbA1c), absolute value and change from baseline visit windows will be calculated from Study Day 1; while toxicity grading summaries will utilize safety analysis visit windows.

For all safety analyses related to laboratory toxicity grading, laboratory data collected up to 30 days after the date of last dose of any study drug will be included.

Visit windows for safety laboratory tests are displayed in the fourth column of Table 3-1.

Analysis Visit	Visit Windows for Hepatic Synthetic Function, Lille Scores, and Recidivism to Alcohol	Visit Windows for Liver Fibrosis Markers	Visit Windows for Vital Signs and Safety Laboratory tests (Hematology, Chemistry, Coagulation, and Lipids)
Baseline	Study $Day \le 1$	Study Day $\leq 1$	Study $Day \le 1$
Week 1	$2 \leq $ Study Day $\leq 10$	N/A	$2 \leq $ Study Day $\leq 10$
Week 2	$11 \leq $ Study Day $\leq 17$	N/A	$11 \leq $ Study Day $\leq 17$
Week 3	$18 \le$ Study Day $\le 24$	N/A	$18 \leq $ Study Day $\leq 24$
Week 4	$25 \leq $ Study Day $\leq 34$	$2 \leq $ Study Day $\leq 55$	$25 \leq $ Study Day $\leq 38$
Week 6	$35 \leq $ Study Day $\leq 48$	N/A	N/A
Week 8	$49 \le $ Study Day $\le 69$	N/A	N/A
Week 12	$70 \le $ Study Day $\le 97$	$56 \leq $ Study Day $\leq 125$	N/A
Week 16	$98 \le $ Study Day $\le 125$	N/A	N/A
Week 20	$126 \le $ Study Day $\le 153$	N/A	N/A
Week 24	Study Day $\ge 154$	Study Day ≥ 126	N/A
FU Week 2	N/A	N/A	$8 \le FU Day \le 20$
FU Week 4	N/A	N/A	$21 \le FU \text{ Day} \le 30$

Table 3-1.A	Analysis Visi	t Windows
-------------	---------------	-----------

Note: Hepatic Synthetic Function includes: ALT, AST, GGT, alkaline phosphatase, total bilirubin, direct bilirubin, albumin, INR, MELD score, CPT score, and Maddrey's DF. Lille scores will only be calculated at Weeks 1, 2, 3 and 4.

Investigator assessment of 12-lead ECG, screening lab tests, and pregnancy tests (for women of child-bearing potential) will be listed using the nominal visit. For shift tables of investigator assessment of the 12-lead ECG, if the baseline/Day 1 visit is missing, the screening value may be used in place of the baseline value. If Week 4 visit is missing, the early study drug discontinuation visit may be used in place of Week 4.

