Subjects whose liver biopsy results are not consistent with AH or whose HIV or hepatitis B or C serologies from the central laboratory are positive must stop study drug within 3 days of receipt of results. In subjects in whom a liver biopsy is insufficient to confirm a diagnosis of AH, subjects may remain in the study if no alternative diagnosis is suggested on biopsy. Subjects whose serum pregnancy testing from the central laboratory is positive at Screening must stop study drug immediately upon receipt of this result. All subjects stopping study drug for inconsistent liver biopsy results, for positive HIV or hepatitis B or C serologies from the central laboratory, or for positive serum pregnancy testing from the central laboratory should attend an EoT visit as soon as possible and have a follow up visit 30 days after their last dose of study drug, prior to being withdrawn from the study (see Sections 6.7 and 6.8 of this protocol for clarification on study drug vs. study discontinuation).

Intensive PK Sub-study

[figure not shown]

Table 3-1. Because biomarker science is a rapidly evolving area of investigation, and adverse events in particular are difficult to predict, it is not possible to specify prospectively all tests that will be done on the specimens provided. The testing outlined is based upon the current state of scientific knowledge. It may be modified during or after the end of the study to remove tests no

longer indicated and/or to add new tests based upon the growing state of the art knowledge. If a test will no longer be performed because the assay is not robust, sample collection may also be withdrawn to reduce burden on subjects.

Specimens will be collected from all subjects. Samples will be destroyed no later than 15 years after the end of the study. The specimen storage period will be in accordance with the IRB/IEC/EC-approved Informed Consent Form (ICF) and applicable laws (eg, health requirements).

Biomarker Focus	Planned Biomarkers	Rational	Specimen Collected
Liver tissue surrogate marker panel	ELF Test	Assess potential changes in liver fibrosis due to treatment	Blood
Liver tissue damage marker	Serum LOXL2	Assess potential changes in liver tissue damage due to treatment	Blood
Apoptosis and Necrosis markers	Circulating Cytokeratin 18 (CK18) fragments, M30 for apoptosis and M65 for all dying cells)	Determine changes in liver cell death due to treatment	Blood

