6.3.4. Week 4 / End of Treatment Visit (EoT) (±3 days)

If the subject meets criteria for discontinuation of treatment (see Section 6.8 of this protocol), the subject should complete an EoT visit as soon as possible after all study drugs are discontinued and attend post-treatment visits as outlined in Appendix 2. Subjects discontinued prior to Week 2 should attend a 30-day FU visit to collect safety data within 30 days of their last dose of study drug. Subjects that have their scheduled Week 4/End of Treatment visit prior to Day 28 will require a phone contact between Study Days 28-35 to assess mortality and liver transplantation.

Subjects should be instructed not to take study drug in the morning of the Week 4 Visit. The dose should be taken as soon as possible after the trough PK (Sparse PK sample collected prior to dosing) and biomarker assessments are completed.

The following will be performed and documented at this visit:

- QoL Questionnaire (CLDQ)
- Assess alcohol consumption
- Complete PE including, vital signs, and body weight
- Perform standard 12-lead ECG
- Assessments for HE, ascites, HRS, and infection.
- Obtain blood samples for:
 - Hematology
 - Chemistry: ALT, AST, albumin, alkaline phosphatase, bicarbonate, BUN, calcium, chloride, creatinine, glucose, LDH, magnesium, phosphorus, potassium, sodium, total and direct bilirubin, total protein, uric acid, GGT. Samples should be drawn for central and local laboratory testing for the calculation of the Lille Score (Section 6.9.12)
 - Coagulation Tests: PT, PTT, and INR
 - Blood and Urine for Biomarkers
 - ELF^{TM} Test and LOXL2
 - Insulin
 - Lipid Profile
 - Sparse PK Sample

- Urine pregnancy test (for females of childbearing potential)
- Collect stool for microbiome testing
- Record all concomitant medications that the subject has taken since the previous visit
- Record any SAEs and all adverse events occurring since the previous visit
- Assess for study drug adherence
- Perform study drug accountability
- FibroScan (if available and for subjects without ascites)
- Record local laboratory results for total bilirubin so that Lille score can be calculated using local laboratory data.

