6.3.5. Follow Up Visit (±5 Days)

Subjects should return for a Follow-Up Visit 30 days after their last dose of study drug.

Subjects whose liver biopsy results are not consistent with AH or whose HIV or hepatitis B or C serologies from the central laboratory are positive, must stop study drug within 3 days of receipt of results. If the liver biopsy sample is inadequate for pathologic diagnosis of AH and no alternative diagnosis is suggested on biopsy, then the subject may remain in the study. Subjects whose serum pregnancy testing from the central laboratory is positive at Screening must stop study drug immediately upon receipt of this result. All subjects stopping study drug for these reasons should attend an EoT visit as soon as possible and have a follow up visit 30 days after their last dose of study drug, prior to being withdrawn from the study. Subjects discontinuing both study drugs prior to Week 2 should complete an end of treatment visit after stopping drug, a 30-day safety FU visit, and all post-treatment follow-up visits. Subjects discontinued after Week 2 should complete an end of treatment assessments as outlined in Appendix 2.

- Record all concomitant medications that the subject has taken since the previous visit
- Record any SAEs and all adverse events occurring since the previous visit
- Assessments for HE, ascites, HRS and infection

- Obtain blood samples for:
 - Hematology
 - Chemistry: ALT, AST, albumin, alkaline phosphatase, bicarbonate, BUN, calcium, chloride, creatinine, glucose, LDH, magnesium, phosphorus, potassium, sodium, total and direct bilirubin, total protein, uric acid, GGT

- Coagulation Tests: PT, PTT, and INR

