#### 7.2. Laboratory Evaluations

Summaries of laboratory data will be provided for the Safety Analysis Set and will include data collected up to the date of last dose of any study drug plus 30 days for subjects who have permanently discontinued study drug. The analysis will be based on values reported in conventional units. When values are below the LOQ, they will be listed as such, and the imputed value will be used for the purpose of calculating summary statistics as specified in Section 3.7.

A by-subject listing for laboratory test results will be provided by subject ID and analysis visit in chronological order for screening tests, hematology, serum chemistry, and coagulation, separately. Values falling outside of the relevant reference range and/or having a severity grade of 1 or higher according to CTCAE toxicity grading will be flagged in the data listings, as appropriate.

No formal statistical testing is planned.

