#### 7.2.2.3. Summaries of Laboratory Abnormalities

The following summaries (number and percentage of subjects) for treatment-emergent laboratory abnormalities will be provided by laboratory test (and direction of abnormality, when applicable) and treatment group; subjects will be categorized according to the most severe postbaseline abnormality grade for a given lab test:

- Grade 3 or 4 laboratory abnormalities
- Marked laboratory abnormalities

For all summaries of laboratory abnormalities, the denominator is the number of subjects with nonmissing postbaseline values up to 30 days after last dosing date.

A by-subject listing of treatment-emergent Grade 3 or 4 laboratory abnormalities will be provided by subject ID number and time point in chronological order. This listing will include all test results that were collected throughout the study for the lab test of interest, with all applicable toxicity grades displayed.

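### A compliant Follow-Up visit on days 31–35 after last dose falls outside the 30-day laboratory limit, so its results enter no toxicity-grade table

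*SAP*

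**What the plan says.** **The visit.** Protocol 6.3.5 states: "Subjects should return for a Follow-Up Visit 30 days after their last dose of study drug". The section heading and Appendix 2 allow ±5 days. Hematology, chemistry and coagulation samples are taken. For subjects discontinued before Week 2, protocol 6.3.4 words the timing differently: they "should attend a 30-day FU visit to collect safety data within 30 days of their last dose of study drug". Subjects stopped because of biopsy, central serology or central pregnancy results "have a follow up visit 30 days after their last dose of study drug, prior to being withdrawn from the study" (protocol 3.2), and protocol 6.7 says they make no further study visits.

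**The analysis limit.** SAP 3.8.2 defines "FU Day = Laboratory assessment date – Last Dose Date of Any Study Drug". In Table 3-1 the last safety laboratory window, FU Week 4, covers FU Days 21 to 30, and no later window exists. For grading, "laboratory data collected up to 30 days after the date of last dose of any study drug will be included". SAP 7.2 says that the safety laboratory summaries "will include data collected up to the date of last dose of any study drug plus 30 days" for subjects who have stopped study drug for good. Sections 7.2.2.1 and 7.2.2.2 apply the same limit to treatment-emergent and marked abnormalities. In section 7.2.2.3, "the denominator is the number of subjects with nonmissing postbaseline values up to 30 days after last dosing date".

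**The protocol's own limit.** Protocol 8.3.1.2, 8.8 and 8.8.3 also end treatment-emergent data, summarised safety data and graded laboratory abnormalities at 30 days after last dose.

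**The concern.** The Follow-Up visit supplies the laboratory sample that closes the 30-day safety period, and safety is the primary endpoint. The scheduling window is centred on the day the analysis window ends, so every compliant visit later than the target day falls outside it. Whether a new Grade 3 or 4 value counts then depends on which permitted day the clinic chose.

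The omission runs in one direction. A subject whose only new Grade 3 or 4 value is drawn on FU Days 31–35 stays in the denominator through earlier post-baseline values and is counted as having no such abnormality. The exposure is greatest for subjects withdrawn after a biopsy not consistent with alcoholic hepatitis, because no later scheduled sample exists for them.

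**Working it through.** The plan gives no figure on this point, so there is nothing to reproduce. The check is a count of days.

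1. **Permitted visit days** (protocol 6.3.5): 30 − 5 = 25 to 30 + 5 = 35, so FU Days 25–35, or 11 days.
2. **Days covered** by Table 3-1 and the grading limit: FU Days 25–30, so 6/11 = 54.5%.
3. **Days not covered:** FU Days 31–35, so 5/11 = 45.5%.
4. **From days to visits.** The documents do not say how visits spread over the window. As an assumption, let visits centre on day 30 with weights proportional to exp(−(d − 30)²/(2·SD²)) for d = 25 to 35. The share after day 30 is then:
   - SD 1 day: 30.1%
   - SD 2 days: 40.0%
   - SD 3 days: 42.9%
   - SD 5 days: 44.5%
   - even spread: 45.5%

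   If sites tend to book early or late, the share could lie outside this range.
5. **Completers**, taking last dose on Study Day 28:
   - Week 6 (Day 42 ± 3) is Study Days 39–45, so FU Days 11–17, inside FU Week 2 (8–20).
   - Week 8 (Day 56 ± 5) is Study Days 51–61, so FU Days 23–33. On 8 of 11 days it can fill FU Week 4; on 3 of 11 (27.3%) it too falls past the limit.
   - FU Days 31–35 are Study Days 59–63, inside the Week 8 efficacy window (49–69). Liver tests, INR and prognostic scores remain eligible there, subject to the rule in SAP 3.8.3 that selects the record closest to the nominal day.
6. **Biopsy withdrawals.** After stopping drug they have the end-of-treatment and Follow-Up visits only. Protocol 4.1 allows up to 20 extra subjects for unconfirmed biopsies, in 120 randomised: 20/120 = 16.7%. This is a planning allowance, not an observed count. These subjects are in the mITT set but not the FAS, so their late liver tests can appear only in the mITT efficacy tables.
7. **What a late sample loses:** toxicity grading for all tests, and the by-visit summaries in SAP 7.2.1 (hematology and non-liver chemistry).
8. **What it keeps:** the by-subject listings in SAP 7.2, and the summaries through Week 24 in SAP 6.2.8. The Grade 3–4 listing in SAP 7.2.2.3 is only a partial safeguard. It shows all results for a test, but it is a listing of treatment-emergent abnormalities, so a late value on its own would not bring a subject into it.
9. **With FU Week 4 ending at FU Day 35:** 11/11 permitted days are covered.

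**The case against.** The strongest reply is that the SAP does what the protocol tells it to do. The 30-day limit is the protocol's treatment-emergent definition, and a tolerance for booking a visit is not an analysis window. This stands. A reader might infer that the SAP departs from the protocol, or that its limit should simply move to +35 days. The documents do not support either. Changing the SAP alone would contradict protocol 8.3.1.2, 8.8 and 8.8.3, would make the statement of no deviations in SAP 7.7 untrue, and would give laboratory data and adverse events different treatment-emergent periods. SAP 2.3 also records that the primary analysis has been done and unblinded, so this would redefine a primary safety analysis after unblinding. For descriptive summaries the reply is weaker: protocol 8.8.3 asks for values at all scheduled time points, and the Follow-Up visit is one.

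A second reply is that the affected group is small. Much of this stands. SAP 4.2.2 records no positive central HBsAg, HCV RNA or HIV results, so no one was withdrawn by that route. Completers have Week 6 and often Week 8 samples in time. Biopsy withdrawals would often stop before Week 2, since protocol 1.5 expects up to 7 days of exposure before the diagnosis is refuted and protocol 3.2 requires stopping within 3 days of the result. For them protocol 6.3.4 would place the visit no later than day 30. But 6.3.5 covers the same subjects and carries the ±5 days, so the protocol does not settle which timing applies.

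A reader might also infer that a visit on FU Days 25–29 ends adverse event collection early, by up to 30 − 25 = 5 days, for subjects then withdrawn. The documents do not go that far. Protocol 7.3 requires collection until 30 days after last dose whatever the visit date. What is missing is a stated contact that completes it; the extra phone contacts cover only mortality and transplantation.

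**Conclusion.** The point holds as a limited mismatch between a visit window and an analysis window, located in both documents. Compliant laboratory samples on 5 of 11 permitted days enter no toxicity-grade table and no by-visit summary of hematology or non-liver chemistry.

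Three stronger readings are tempting and not supported. The data are not discarded: the values are listed, and the liver-related ones are also summarised. The 45% is a share of calendar days, not of visits or of subjects; the 30% to 45% range for visits rests wholly on the assumption that they centre on day 30. And nothing in the documents suggests that visit timing differs between the blinded arms, so no bias in the treatment comparison is shown.

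The number of Grade 3–4 values missed cannot be estimated, because the documents give neither visit dates nor event rates. The conclusion assumes that some subjects attended on FU Days 31–35. The existing listings can show whether any did.

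**What to change.** - **Table 3-1:** extend the descriptive FU Week 4 window to 21 ≤ FU Day ≤ 35, with a matching exception in SAP 7.2 for by-visit summaries. No later FU window exists, so nothing overlaps.
- **Grading:** keep +30 days as the primary treatment-emergent definition. Add supplementary versions of the Grade 3–4 and marked laboratory abnormality tables that include scheduled Follow-Up visit values through FU Day 35, with the denominator extended to match.
- **SAP 7.7:** record both changes as additions made after the primary analysis.
- **Protocol:** reconcile the timing in 6.3.4 with the ±5 days in 6.3.5, and both with the 30-day adverse event collection period for subjects whose last contact falls on FU Days 25–29. SAP 2.3 says every subject had completed the later of the 30-day visit and Week 8, or had left the study, by the primary analysis. This step therefore documents which timing was in force and cannot change conduct.

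The cost is a few lines of SAP text and one or two extra tables, which carry up to 5 more days of off-drug data and should be labelled so. No new data collection is needed.
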